In the dose escalation phase (Cohorts 1 through 5 only) and the dose expansion phase, in Cycle 2 and beyond, a dose can be delayed up to 7 days based on hematologic and nonhematologic toxicities, according to the conditions described in Section 3.5.5, but all 3 doses (Cohorts 1 through 5 and the dose expansion phase) must be completed within the cycle in order for the cycle to be considered complete. Subjects who do not receive all required doses within a cycle will not advance to the next cycle and will be removed from treatment. Each new cycle will begin 7 days after the last dose of the previous cycle (Cohorts 1 through 5 and the dose expansion phase). Subjects in Cohorts 6 and 7 cannot have a delay in treatment due to hematologic or nonhematologic toxicities. For Cohorts 1 through 5 and the expansion phase, all visits during Cycle 2 and subsequent visits may occur in a ± 2 -day window to accommodate schedule changes, but doses of MEDI-573 must not occur more frequently than every 6 days. For Cohorts 6 and 7 (if applicable), all visits during Cycle 2 and subsequent visits may occur in a + 2-day window to accommodate schedule changes, but dosing of MEDI-573 must not occur more frequently than every 21 days.

Treatment with MEDI-573 will continue until unacceptable toxicity, documentation of disease progression, or other reasons for subject withdrawal. Rules for dose-escalation are described in Section 4.9. Intra-subject dose-escalation will not be allowed. Dose reduction for toxicities other than DLTs will be allowed as described in Section 3.5.5.

Table 3.5.2-1 Summary of Dose Cohorts

Dose Cohort	Number of Subjects	MEDI-573 Dose
1	3-6	[REDACTED] IV infusion once every 7 days
2	3-6	[REDACTED] infusion once every 7 days

Table 3.5.2-1 Summary of Dose Cohorts

Dose Cohort	Number of Subjects	MEDI-573 Dose
3	3-6	██████████ IV infusion once every 7 days
4	3-6	██████████ IV infusion once every 7 days
5	3-6	██████████ IV infusion once every 7 days
6	3-6	██████████ V infusion once every 21 days
7 (if applicable)	3-6	██████████ IV infusion once every 21 days
Dose-expansion	Up to 20	██████████ IV infusion once every 7 days

IV = intravenous

Note: The dose-expansion phase will evaluate PK and pharmacodynamic parameters and determine tumor response in approximately 20 subjects with advanced urothelial carcinoma (eg, bladder cancer).

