Blood biomarker analysis	X	X	X ^b

^a For subjects who discontinue treatment due to reasons other than disease progression or initiation of alternative anticancer therapy, disease evaluations will be performed every 3 months until documentation of disease progression, initiation of alternative anticancer therapy, or the end of study (defined as 1 year after the last subject enters the study). Physical examination is focused for purposes of disease evaluation.

^b This test will only be performed at 3 months post dose.

Table 3.6-4 Summary of Biopsy Collection

Specimen	Dose-Escalation Phase		Dose-Expansion Phase	
	Specimen to be Collected?	Timing of Collection (relative to treatment)	Specimen to be Collected?	Timing of collection (relative to treatment)
Archived tumor biopsy	YES [voluntary]	N/A	YES [voluntary]	N/A
Biopsy in the course of routine clinical care	YES [voluntary]	As clinical care may dictate	YES [voluntary]	As clinical care may dictate
Urothelial cells	NO	N/A	YES [voluntary]	When possible if obtained in the course of urologic procedure; otherwise part of standard urine collection
Biopsy of bladder cancer or bladder cancer metastasis	NO	N/A	YES [required]	Pre-treatment & before C2D1 ^a

N/A = not applicable

^a Samples will be collected at two timepoints: prior to the first treatment of Cycle 1, and after the last dose of Cycle 1 but prior to administration of the first dose of Cycle 2.

Screening (All Subjects Unless Otherwise Specified)

Note: All screening laboratory assessments must be performed within 28 days before study entry (Study Day 1), unless otherwise specified. The screening evaluations may be carried out over more than 1 visit. Written informed consent and HIPAA (applies to covered entities in the USA only) must be obtained prior to performing any study-related procedure, including screening evaluations. However, if evaluations that have been performed for other purposes prior to informed consent are otherwise suitable for use as screening evaluations, those studies need not be repeated if the subject/legal representative consents to allow use.

- 1) Written informed consent and HIPAA
- 2) Obtain SID from Sponsor
- 3) Verify eligibility criteria
- 4) Medical history
- 5) Perform complete physical examination

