The following evaluations will be performed every 2 cycles (ie, every 6 weeks), unless otherwise indicated, starting at Cycle 3 (eg, Cycle 3, Cycle 5, etc.):

- 1) Complete physical examination
- 2) AE/SAE assessment
- 3) Concomitant medications
- 4) Evaluation of disease
 - CT or MRI scans

End of Treatment (All Subjects Unless Otherwise Specified)

The following evaluations will be performed at the time the subject completes therapy or is withdrawn / discontinued from the study therapy, or at the time of the first objective disease progression, whichever comes first. These procedures do not need to be repeated if completed within 14 days of discontinuation of participation.

- 1) Complete physical examination
- 2) Weight
- 3) Vital signs
- 4) Blood and tissue collection
 - Hematology (CBC with differentials, platelets, and HgA1c)
 - Serum chemistry (AST/ALT, total bilirubin, creatinine, alkaline phosphatase, sodium, potassium, chloride, phosphorus, calcium, glucose, albumin, magnesium, LDH, TSH)
 - Serum concentration of MEDI-573
 - Blood biomarker analysis
 - Whole blood RNA analysis
 - Circulating tumor cells
 - Urinalysis (routine urinalysis with microscopy)
 - Exfoliated urothelial cells and analysis of soluble factors (from urine or bladder washes; dose-expansion cohort only)
- 5) AE/SAE assessment
- 6) Concomitant medications

- 7) ECG (12-lead). All ECGs performed will be obtained in triplicate, ie, 3 ECGs should be obtained within approximately a 5-minute time interval.
- 8) Disease evaluations (these procedures do not need to be repeated if they have been performed within 14 days of disease progression or treatment discontinuation)
 - CT or MRI scans
 - Physical examination
 - Karnofsky performance status

21 Days Post-therapy (+ 3 days; All Subjects)

- 1) Serum concentration of MEDI-573
- 2) Blood biomarker analysis

30 Days Post-therapy (+ 3 days; All Subjects)

The following evaluations will be performed at 30 days (+ 3 days) after the last dose of MEDI-573:

- 1) Complete physical examination
- 2) Weight
- 3) Vital signs
- 4) ECG (12-lead) All ECGs performed will be obtained in triplicate, ie, 3 ECGs should be obtained within approximately a 5-minute time interval.
- 5) Blood collection
 - Hematology (CBC with differentials, platelets)
 - Serum chemistry (AST/ALT, total bilirubin, creatinine, alkaline phosphatase, sodium, potassium, chloride, phosphorus, calcium, glucose, albumin, magnesium, LDH, and TSH)
 - Serum concentration of MEDI-573

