 - Anti-MEDI-573 antibodies
 - Blood biomarker analysis
- 6) Urinalysis (routine urinalysis with microscopy)
- 7) Urine β hCG (women of child bearing potential only)
- 8) AE/SAE assessment
- 9) Concomitant medications
- 10) Karnofsky performance status

- 11) Subsequent anticancer therapy

Survival Follow-up / Every 3 Months Post-Therapy (\pm 2 weeks; All Subjects)

The following evaluations will be performed every 3 months (\pm 2 weeks) after the last dose of MEDI-573 as specified:

- 1) Complete physical examination
- 2) Evaluation of disease (subjects who discontinue treatment due to reasons other than disease progression or initiation of alternative anticancer therapy; these evaluations will be performed until documentation of disease progression, initiation of alternative anticancer therapy, or the end of study [defined as 1 year post entrance of the last subject into the study])
 - CT or MRI scans
 - Karnofsky performance status
- 3) Anti-MEDI-573 antibodies (this test will only be performed at 3 months after the last dose of MEDI-573 for all subjects)
- 4) Serum concentration of MEDI-573 (this test will only be performed at 3 months after the last dose of MEDI-573 for all subjects)
- 5) Blood biomarker analysis (this test will only be performed at 3 months after the last dose of MEDI-573 for all subjects)
- 6) Survival status and subsequent anticancer therapy by clinic visit or telephone contact until subject death or end of the study (all subjects).

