3.8 Completion of Study and Loss to Follow-up

Subjects alive at the end of the study will be considered to have completed the study if they were followed until the end of the study (defined as 1 year after the last subject entered the study). It should be specified on the source document whether or not the subject completed the study follow-up procedures through the end of the study.

Subjects will be considered lost-to-follow-up only if no contact has been established by the time the study is completed such that there is insufficient information to determine the subject's status. Investigators should document attempts to re-establish contact with missing

subjects throughout the study period. If contact with a missing subject is re-established, follow-up should resume according to the protocol.

4 Safety Assessment

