4.7 Interruption or Discontinuation of Study Dosing in Individual Subjects

An individual subject will not receive any further investigational product if any of the following occur in the subject in question:

- 1) Withdrawal of consent
- 2) Grade 2 or greater allergic reactions. Grade ≤ 3 infusion reactions that respond to medical therapy or slowing the infusion rate and are of limited duration will not necessitate dose interruption or discontinuation. Any infusion or allergic reaction that necessitates the use of systemic pressor agents will cause dose discontinuation in that subject.
- 3) Pregnancy or intent to become pregnant
- 4) DLT (see Section 4.10 for definition of DLTs, dose escalation phase only).
- 5) Occurrence of Grade 3 or Grade 4 hematologic or non-hematologic toxicity after the first cycle of treatment
- 6) Grade ≥ 2 toxicities (after completion of Cycle 1) that do not return to Grade ≤ 1 or baseline within 7 days unless clearly attributable to other causes such as disease progression or accident.
- 7) Grade ≥ 2 toxicities that cause a cumulative delay of ≥ 21 days in 3 consecutive cycles (Cohorts 1 through 5 and the expansion phase)
- 8) Documentation of disease progression

- 9) Event which in the opinion of the investigator contraindicates further dosing such as intercurrent illnesses, significant drug toxicities or complications if judged by the investigator to be in the best interest of the subject
- 10) Subject non-compliance
- 11) Treatment with another investigational agent
- 12) Initiation of alternative anticancer therapy

Subjects who are permanently discontinued from investigational product will be followed for the full study period (through 30 days after the last dose of MEDI-573), including the collection of any protocol-specified blood and urine specimens, unless consent is withdrawn.

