Overall survival (OS) will be determined as the time from the start of treatment with MEDI-573 until death. For subjects who are alive at the end of study or lost to follow-up, OS will be censored on the last date when subjects are known to be alive.

The time to event data including TTR, DR, TTP, PFS, and OS will be evaluated using Kaplan-Meier methods.

6 Data Collection and Monitoring

The study will be monitored by the Sponsor or its designee on a regular basis throughout the study period. During monitoring visits, the investigator will provide direct access to all source documentation relevant to the subject's participation in the study. Source documentation includes, but is not limited to, the subject's clinic and/or office chart, hospital chart, informed consent forms, treatment notes, laboratory reports, pharmacy records, radiographs, and any other records maintained to conduct and evaluate the clinical study. The investigator must also ensure that direct access to study documents be made available for study-related audits, IRB/IEC review, or regulatory inspection.

Data recorded on source documents will be transcribed onto a validated data collection instrument (a paper case report form or electronic data screen) provided by the Sponsor or

designee. The investigator must ensure the accuracy and completeness of the data reported, and its consistency with the source documentation.

The primary source document for this study will be the subject's medical record. If separate research records are maintained by the investigator(s), both the medical record and the research records will be monitored/audited for the purposes of the study.

Study documents (including subject records, copies of collected data, study notebook, and pharmacy records) must be kept secured in accordance with Sponsor policies and applicable regulatory requirements for a period of 2 years following marketing of MEDI-573 or for 2 years after centers have been notified that the IND has been discontinued. There may be other circumstances for which the Sponsor is required to maintain study records and, therefore, the Sponsor should be contacted prior to removing study records for any reason.

7 Human Subjects

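### Section 4.7 ends follow-up of discontinued subjects 30 days after the last dose, against the schedule and the end-of-study definition; separately, scans every 2 cycles are every 6 weeks only when no dose is delayed

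*Protocol*

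**What the plan says.** **Length of follow-up.** The closing paragraph of Section 4.7 states that subjects permanently discontinued from MEDI-573 "will be followed for the full study period (through 30 days after the last dose of MEDI-573"), including any blood and urine specimens the protocol specifies. The survival follow-up list in Section 3.6 requires "Survival status and subsequent anticancer therapy by clinic visit or telephone contact until subject death or end of the study (all subjects"). Section 3.8 counts living subjects as having completed the study if they were "followed until the end of the study (defined as 1 year after the last subject entered the study"). Footnote a of Table 3.6-3 covers subjects who stop for reasons other than progression or new anticancer therapy: "disease evaluations will be performed every 3 months until documentation of disease progression", new therapy or end of study. Footnote b, on the serum concentration, antibody and biomarker samples in the 3-monthly column, reads "This test will only be performed at 3 months post dose".

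**Scan timing on treatment.** Section 3.6 states: "The following evaluations will be performed every 2 cycles (ie, every 6 weeks), unless otherwise indicated". CT or MRI is among these evaluations. For Cohorts 1 to 5 and the expansion phase, Section 3.5.2 lets a dose slip by up to 7 days for toxicity from Cycle 2, requires all three doses within the cycle, and adds: "Each new cycle will begin 7 days after the last dose of the previous cycle". Section 4.7 item 7 stops treatment once toxicity delays total 21 days or more in 3 consecutive cycles. Cohorts 6 and 7 may not delay for toxicity.

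**The concern.** Treatment continues until toxicity, progression or withdrawal, so nearly every subject eventually comes under the Section 4.7 sentence. It describes the 30 days as the whole study period, not as a safety reporting window. A site that stops there would not collect later survival status, off-treatment scans or 3-month samples, and some of these cannot be recovered afterwards. OS, off-treatment PFS, late drug concentrations and immunogenicity would all be affected.

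The scan rule raises a different problem. TTP and PFS are dated from documented progression (Section 5.4.4), so progression is recorded when someone looks. If the next scan moves back whenever a dose is delayed for toxicity, the recorded date reflects tolerability as well as tumor growth.

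**Working it through.** **1. Follow-up: the passages side by side**

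| Item | Section 4.7 | Section 3.6, Table 3.6-3, Section 3.8 |
|---|---|---|
| Survival status | 30 days after last dose | every 3 months to death or end of study, all subjects |
| Disease evaluation after stopping without progression or new therapy | 30 days after last dose | every 3 months to progression, new therapy or end of study |
| Serum drug, antibody and biomarker samples | 30 days after last dose, yet all specified specimens to be collected | also at 3 months |
| End point | last dose + 30 days | last subject's entry + 1 year |

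The two columns cannot both be followed. Section 4.7 also conflicts with itself: with visits at 3 months ± 2 weeks (91 ± 14 = 77 to 105 days), three specimen types fall due after day 30. The OS rule in Section 5.4.4, "OS will be censored on the last date when subjects are known to be alive", applies to subjects alive at end of study or lost to follow-up, so it presupposes the longer horizon.

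Conditional illustration, only for subjects whose follow-up stopped at day 30. Assume exponential survival after the last dose with median m months (not given in the protocol). The share dead by day 30 is 1 − 2^(−30/(30.4375·m)): 20% for m = 3, 11% for m = 6, 5.5% for m = 12. Later deaths would go unseen.

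**2. Scan interval, Cohorts 1 to 5 and expansion**

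- Plan's figure: 2 × 21 = 42 days = 6 weeks. It reproduces with no delay.
- Strict reading, all three doses within 21 days of the cycle's scheduled Day 1: the last dose can slip from Day 15 to Day 21, and the next cycle starts on Day 28 instead of Day 22, which is 6 days late. Two cycles take 42 + 6 = 48 days if one cycle slips, and 42 + 12 = 54 if both do.
- Looser reading, limited only by 7 days per dose and the item 7 cap: the total must stay below 21, so at most 20 whole days. One full delay gives 49 days, two give 56, and the cap gives 42 + 20 = 62 (62/42 = 1.48).
- First scan: only Cycle 2 can slip, so the maximum is 48 days on the strict reading. Reaching 62 needs Cycle 2 delays of 7 + 7 + 6.
- Sustained delay: the cap allows 20 days per 3 cycles, so the long-run average is at most 42 + 20 × 2/3 = 55.3 days. The 62 days is a maximum for a single interval.

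Cohorts 6 and 7 stay at 42 days, apart from their +2-day visit window.

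**3. What this does to recorded dates (illustration)**

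Assume exponential true progression times with median m = 42 to 126 days (not in the protocol) and a constant scan interval L. With λ = ln 2/m, mean detection lag = L/(1 − e^(−λL)) − 1/λ. For m = 84, 1/λ = 121.2:

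- L = 42: 42/0.2929 − 121.2 = 22.2 days
- L = 62: 62/0.4005 − 121.2 = 33.6 days

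Over the whole range of m, the lag is 21.8 to 23.4 days at L = 42, 29.4 to 32.3 at L = 56 and 32.8 to 36.2 at L = 62. Near the sustainable limit (L = 56), delay therefore adds about 8 to 9 days on average. The 11 to 13 days implied at L = 62 is an upper illustration, because that interval cannot recur every time.

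**The case against.** On follow-up, Section 4.7 sits in the safety chapter, and its 30 days match the AE and SAE reporting windows in Sections 4.1.2 and 4.2.2. Section 3.6 says all dosed subjects are followed according to the protocol however many doses they receive. A reader might infer from Section 4.7 that OS is truncated in this trial. The documents do not support that: survival status to death or end of study is required for all subjects, and the OS rule uses that horizon. Loss arises only where Section 4.7 is allowed to override those sections. The contradiction stands, because Section 4.7 calls the 30 days the full study period and names specimens it would then exclude.

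On scans, a reader might infer that TTP and PFS are biased in favor of higher doses. That does not follow. Section 5.4.4 specifies Kaplan-Meier methods without calling for by-cohort TTP or PFS. Cohorts 6 and 7 cannot delay for toxicity. Section 1.5 reports no DLTs in the first 17 subjects and treatment-related events of Grade 1 or 2 only, so no toxicity gradient by dose is shown. An End of Treatment scan is required unless one was done within 14 days, which limits the lag at discontinuation and can bring a scan forward. The 3-monthly imaging after that is a design choice. These are descriptive secondary endpoints in a single-arm study, and no decision rule uses them. What remains is that the six-week statement fails under either reading of the delay rules and that scan dates move with toxicity.

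**Conclusion.** Both points hold, with limits. The follow-up contradiction is textual and needs no assumption. Its effect is conditional: survival, off-treatment PFS and 3-month sample data are lost only where a site follows Section 4.7 literally.

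The scan interval in Cohorts 1 to 5 and expansion is 42 days without delay, 48 to 54 when delays use the full strict allowance, and at most 62 on the looser reading. The average effect on recorded TTP and PFS is a matter of days and rests on assumed progression times. No direction by dose is established, and neither the primary endpoints nor the escalation rules are touched. Both are worth correcting in the protocol itself, since it is the protocol that fixes visits and scan dates.

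**What to change.** In Section 4.7, replace the parenthesis so that the 30 days apply to AE/SAE follow-up only, and refer to Table 3.6-3 and Section 3.8 for survival status, disease evaluation and the 3-month samples. The SAE follow-up to resolution in Section 4.2.2 stays as it is.

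In Section 3.6 and Tables 3.6-1 and 3.6-2, schedule on-treatment tumor assessments every 6 weeks from Cycle 1 Day 1, within a stated window and regardless of dose delays. Align the matching sentences in the Study Abstract and Section 2.4. The other evaluations now due every 2 cycles can stay tied to the cycle.

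The cost is amendment wording. The downside is that, after a delay, a scan may not coincide with a dosing visit. No dose, delay or stopping rule changes.

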4.8 Interruption or Discontinuation of Study Dosing and Entry

If any of the following occur, no further administration of investigational product will take place and no further subjects will be entered into the study:

- 1) Death in any subject in which the cause of death is assessed as possibly, probably, or definitely related to investigational product;
- 2) Anaphylactic reaction to investigational product in any subject; or
- 3) Other events that in the judgment of the Medical Monitor are serious enough to warrant immediate review by the MedImmune Safety Monitoring Committee (SMC).

If one of the above-listed events occurs, a prompt cumulative review of safety data and the circumstances of the event in question will be conducted by the medical monitor and the MedImmune SMC to determine whether dosing and study entry should be resumed, whether the protocol will be modified, or whether the study will be discontinued permanently. Review and approval by the MedImmune SMC are required for resumption of the study in the event the study is interrupted because of one of the above-listed events.

4.9 Dose Escalation and Dose Expansion

Rules for dose-escalation are as follows:

- 1) Dose-escalation will begin with a single subject in each cohort. If no DLTs (as defined in Section 4.10) are observed in this subject within the first 7 days of administration of MEDI-573, two additional subjects will be enrolled into that cohort and may be dosed immediately.
- 2) If no DLTs are observed in the first 3 subjects treated in the cohort through the first 21 days of administration of MEDI-573, enrollment in the next higher cohort will begin using the same rules described in Item 1.

Note: The decision to continue enrollment into Cohort 7 [REDACTED] will be based on the sponsor's assessment of PK, pharmacodynamic, IM, and safety data.

- 3) If 1 out of 3 subjects within a cohort experiences a DLT during the first 21 days of administration of MEDI-573, that cohort will be expanded to a total of 6 subjects provided no further subject experiences a DLT. If no further subjects experience a DLT through the first 21 days of administration of MEDI-573 in the expanded cohort, dose-escalation will continue in the next higher cohort using the same rules described in Item 1.
- 4) If 2 or more subjects within a cohort experience a DLT within the first 21 days of administration of MEDI-573, then the MTD will be exceeded and no further subjects will be enrolled into that cohort. If this happens, the preceding cohort will be evaluated as the MTD, with three additional subjects if this cohort has not previously been expanded to six subjects. If ≤ 1 of 6 subjects experience a DLT, this cohort shall be declared the MTD.
- 5) The decision to enroll the next higher cohort or to continue enrollment in the current cohort will be jointly made following a meeting or teleconference attended by all investigators, the medical monitor, a MedImmune Patient Safety physician and optional attendance of the therapeutic area head. A representative from clinical operations will document the discussion and decision. Treating investigators will provide a verbal or written summary of treatment including description of any adverse events. If a treating investigator is unable to attend, a written summary of findings will be submitted. A decision will not be reached unless all treating physicians have attended the meeting or teleconference or submitted a written summary. Dose-escalation will not proceed until approved by the Sponsor.

Twenty subjects with bladder cancer will be treated in the dose-expansion phase. Subjects enrolled in the dose-expansion phase of the study who consent will have archived tumor biopsies and/or biopsies obtained during surgical procedures conducted in the course of routine patient care. These subjects will provide cells collected in voided urine, catheterized urine, or bladder washings (optional), in addition to other scheduled evaluations. The dose for the expansion phase will be determined as follows:

- 1) Two cohorts of approximately 10 subjects each will be examined in the dose-expansion phase [REDACTED] every 7 days. The first 10 subjects enrolled into the dose-expansion phase will receive doses of MEDI-573 [REDACTED] every 7 days. The decision to continue enrollment of subjects in the lower [REDACTED] dose-expansion cohort will be based on pharmacodynamic assessments of tissue obtained from subjects pre- and post-exposure to MEDI-573 at [REDACTED] dose level. In the event there is insufficient activity at the tissue level in the higher dose-expansion cohort, the sponsor may halt dose-expansion and no additional subjects will be enrolled into the expansion phase

- 2) At the discretion of the Sponsor, an intermediate dose may be chosen for the dose-expansion phase of the study. Situations that might prompt selection of an intermediate dose include unexpected toxicities that do not meet definition of DLT or multiple similar toxicities in a cohort that do not meet the definition of a DLT.

